## **3.Research idea (working hypothesis)**

Modern rehabilitation theory shows that the functional system of

the central nervous system has the ability of plasticity and re after craniocerebral injury, and appropriate stimulation is conducive to the reinnervation of nerves. Median nerve electrical stimulation (MNES) is a cutting- treatment modality clinically for the treatment of coma, and gradually favored by experts at home and abroad, because of its significant advantages such as simplicity, effectiveness and non-invasiveness promoting awakening, and has reached rapid development and popularization in recent years. Its mechanism is to act on the reticular ascending activation system of the brainstem by low-frequency pulse stimulation (usually twice a day of median nerve electrical stimulation treatment, lasting for 60 minutes, lasting for about 8 weeks), to maintain the excited state of the cere cortex, stimulate nerve cells in various parts of the cerebral cortex, promote the release of acetylcholine, and maintain the state of awakening of the cerebral cortex.

The treatment of diseases by auricular acupoints has been documented in ancient Chinese literature. It is written in the "M Question Chapter" of "Yellow Emperor's Inner Canon: Ling Shu" that "the ear is the place where the main meridians gather" and "the meridians connect to the ear." Stimulating auricular acupoints can regulate the functions of the related meridians, playing a role in the circulation of and blood, and regulating the yin and yang of the zang-fu organs. The

therapy of pressing needle has been demonstrated in the book "Su Wen: Hetong Zhen Ye Lun", which advocates the "static and long-term retention" of pressing needle. Auricular pressing needle therapy is a method of inserting and fixing specific type of small needle into the auricular acupoints for a longer period. By applying a steady and stable stimulus to the auricular acupoints with needles, it can achieve the effect of smoothing the meridians and collaterals, and regulating the yin and yang of the zang-fu organs. It has advantages in improving the function of consciousness. The long-term feature of auricular pressing needle treatment makes up for the shortcomings of the short action time and long cycle of median electrical stimulation, making the stimulation continuous and stable, which can greatly reduce the treatment cycle and is more conducive to improving the disturbance of consciousness in patients.

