##### **1.3 Termination and handling of the trial**

In the course of the trial, those who have serious adverse events, or serious complications or worsening of the condition should be immediately removed from the clinical trial by the doctor. When the case is

stopped, the doctor should immediately give symptomatic clinical treatment. After the case is stopped, the doctor should investigate and record cause, retain the case observation data, and take the last detection result as the final result, and conduct data analysis on the efficacy and adverse reactions.

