## **2. Intervention measures**

2.1 Control group: Conventional treatment methods were adopted, including surgery, drug therapy, nutritional support, Chinese medicine, and acupuncture, as well as prevention of complications. Meanwhile, median nerve electrostimulation (Shenzhen Dongdi Xin Technology Co., Ltd, MT1023 multifunctional electrotherapy comprehensive treatment instrument) was combined, with two treatments per day (skin electrodes were placed 2cm above the wrist transversease on the anterior aspect of the right forearm, using direct current asymmetric rectangular wave, stimulation intensity of 20mA, pulse width of 300ms, frequency 40Hz, working for 20 seconds per minute, resting for 40 seconds, generally lasting for 60 minutes, and lasting for about 8 weeks.

2.2 Experimental group: In addition to conventional rehabilitation treatment methods and median nerve electrostimulation, auricular acupuncture was combined, with acupuncture at heart, Shenmen, sympathetic, and subcortical points (Suzhou Medical Supplies Co., Ltd., Hua Tuo brand disposable sterile push acupuncture model 0.20×0.8mm).

The family members were instructed to massage each acupoint three times a day, each time for 10 minutes with moderate pressure, each treatment for 3 days, rest for 1 day, repeat three times, a total of 11 days in one course of treatment.

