### **3. Observation indicators**

After 4, 6, and 8 weeks of continuous intervention, the awakening conditions, including GCS, GOS outcome evaluation, CRS-R scores, and family satisfaction, were compared.

3.1 Awakening conditions: The time of patient awakening and the awakening at 4, 6, and 8 weeks after intervention were recorded.

3.2 The GCS scale (Glasgow Coma Scale) includes three dimensions: opening, language, and motor, with a full score of 15 points. The lower the score, the worse the patient's neurological function recovery.

3.3 CRS-R (Coma Recovery Scale-Revised): It adds evaluation content such as arousal response, communication ability, and auditory level compared to the GCS scale. lowest score is 0, and the highest score is 23. The higher the score, the higher the level of consciousness.

3.4 Prognosis evaluation was at 1 month after treatment based on the Glasgow Outcome Scale (GOS). A score of 5 indicates good recovery, 4 indicates moderate disability, 3 indicates disability, 2 indicates a vegetative state, and 1 indicates death.

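### GOS is given two timings with no stated relation between them, and the prognosis reading has no fixed day from randomisation

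*Combined protocol and SAP*

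**What the plan says.** All places are in the Combined protocol and SAP.

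- **Section 3, Observation indicators, lead sentence:** "After 4, 6, and 8 weeks of continuous intervention, the awakening conditions, including GCS, GOS outcome evaluation, CRS-R scores, and family satisfaction, were compared". GOS is one of the measures named.
- **Same section, item 3.4:** "Prognosis evaluation was at 1 month after treatment based on the Glasgow Outcome Scale (GOS". No window is given, and no day counted from randomisation or injury.
- **Section 2, Intervention measures, 2.1:** median nerve stimulation is described as "generally lasting for 60 minutes, and lasting for about 8 weeks". Under 2.2 the experimental arm receives the ear needles on top of this stimulation. The ear course is "each treatment for 3 days, rest for 1 day, repeat three times, a total of 11 days in one course of treatment", and the number of courses is not stated.
- **Section 1.3, Termination and handling of the trial:** for patients taken out because of a serious adverse event, a serious complication or deterioration, the plan is to "take the last detection result as the final result".

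No sentence links the lead sentence to item 3.4, says which GOS reading is the prognosis outcome, or defines treatment for the purpose of item 3.4.

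**The concern.** Patients enter within 10 days of injury with a GCS of 4 to 8. Their state can be expected to change over the following weeks, so a GOS score means little without the time at which it was read.

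Three things are at stake:

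- **Choice of reading.** Up to four GOS readings fit the text (three in the lead sentence, one in item 3.4) and none is named as the prognosis outcome. With 30 patients per arm and a P<0.05 rule, the reported one could be chosen after the data are seen. Correcting for multiple tests would not cure this: a single GOS test would still lack a date.
- **Anchor.** Item 3.4 counts from the end of treatment, which happens after randomisation and is known only approximately.
- **Mixed dates.** Removed patients contribute an earlier value than completers. They are removed because they are doing badly, so their later status is what a prognosis outcome should capture. GOS scores death as 1. A patient removed for deterioration who dies later would keep the last score recorded while alive.

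**Working it through.** **Inputs.** Visits at 4, 6 and 8 weeks (section 3, lead sentence); 1 month after treatment (item 3.4); about 8 weeks of stimulation (2.1); 11 days per ear course (2.2). Assumptions: 1 month is 30 days, and days are counted from the start of intervention, taken to be at or close to randomisation.

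**Step 1. Reproduce the plan's own figure.** The only treatment length that can be recomputed is the ear course: 3 blocks × 3 days + 2 rest days between blocks = 11 days. This agrees with the plan.

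**Step 2. Lead-sentence dates.** 4 × 7 = 28, 6 × 7 = 42, 8 × 7 = 56.

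**Step 3. Item 3.4 date.** GOS day = last day of treatment + 30.

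| Length of stimulation | Last day | GOS day | Week |
|---|---|---|---|
| 7 weeks (assumed low end) | 49 | 79 | 11.3 |
| 8 weeks | 56 | 86 | 12.3 |
| 9 weeks (assumed high end) | 63 | 93 | 13.3 |

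For completers the spread is 93 − 79 = 14 days. The 7-to-9-week range is an assumption; the plan says only "lasting for about 8 weeks".

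**Step 4. Can the two timings be the same visit?** For item 3.4 to fall on day 28, 42 or 56, treatment would have to end on day 28 − 30 = −2, 42 − 30 = 12 or 56 − 30 = 26. None fits about 8 weeks. At exactly 8 weeks, item 3.4 falls 86 − 56 = 30 days after the last lead-sentence visit.

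**Step 5. Could the wording be loose?** Item 3.1 says "The time of patient awakening and the awakening at 4, 6, and 8 weeks after intervention were recorded", using after intervention for weeks that the lead sentence places during it, so translation may play a part. If item 3.4 meant 1 month from the start of treatment, it would fall near day 30, close to the week-4 visit. The GOS comparisons at weeks 6 and 8 would still be unexplained.

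**Step 6. Removed patients.** Under section 1.3 the last result stands as final. A patient removed between weeks 4 and 6 would carry a week-4 GOS (day 28), if GOS is read then, to be set beside completers' readings at about day 86. A patient removed before week 4 has no post-baseline GOS scheduled in section 3. The before-and-after comparison in section 4, Statistical treatment, implies some baseline measurement, but the plan does not say that GOS is included.

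**The case against.** The strongest reply is that readings at weeks 4, 6 and 8 followed by one reading a month after treatment form an ordinary serial schedule. Nothing excludes it. A reader might infer that the two timings cannot both be the plan; the text does not support that. What remains is that the plan neither states such a schedule nor says which reading is the prognosis outcome.

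Second, both arms nominally have about 8 weeks of stimulation, so on the plain reading item 3.4 falls near week 12 in each. A reader might infer that the arms are scored at different times and that the GOS comparison is confounded with time. The documents do not show this. Three supports for that inference fail:

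- **Counting from the ear course.** One course plus 30 days gives 11 + 30 = day 41. But this takes treatment to mean a single ear course, which controls never receive and which may be repeated in the experimental arm.
- **Treatment ending at awakening.** No section contains such a rule. The remark in section 3, Research idea, that the ear needles make stimulation continuous, "which can greatly reduce the treatment cycle", is rationale and does not set a stopping point.
- **Scoring stopped patients a month after they stop.** Section 1.3 takes their last result instead.

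Third, the 86 − 28 = 58 days between the first lead-sentence visit and item 3.4 should not be read as uncertainty in one outcome's date. It is largely the gap between visits that may all be planned.

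Finally, the plan does not name GOS as primary, and its stated objective is recovery of consciousness. That limits the weight of the point. It does not remove the need to date an outcome that the plan intends to compare.

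**Conclusion.** The point holds as a gap in the definition of the GOS outcome. The plan gives two timings that do not coincide under its own treatment length (days 28, 42 and 56 against about day 86) and does not relate them. For completers, the item 3.4 date is uncertain by about two weeks (days 79 to 93) if about 8 weeks means 7 to 9. For removed patients the final GOS is earlier, or may be absent if removal precedes week 4.

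A difference in timing between arms is a risk, because nothing fixes a common date, but it is not shown. It could arise if the actual length of treatment, or the number or timing of removals, differed between arms. No sample-size or power figure is affected. The conclusion rests on a 30-day month and on intervention starting at or near randomisation. It is a worthwhile and inexpensive correction.

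**What to change.** Reconcile the lead sentence of section 3 with item 3.4, and amend section 1.3:

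1. In item 3.4, name one GOS prognosis assessment at a fixed time from randomisation, with a stated window that is the same in both arms. About 12 weeks would match the plan's own 8 weeks plus 1 month.
2. In the lead sentence, delete GOS from the 4-, 6- and 8-week list or label those readings descriptive.
3. In section 1.3, state that removed patients are still scored for GOS on that date, with death scored as 1, in place of taking the last result as final for this outcome.

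This concerns only when the outcome is assessed and changes no rule on treatment or on stopping it. The cost is two short text changes, one in section 3 and one in section 1.3, and following removed patients to a visit that item 3.4 already plans. That follow-up is the only real extra work.

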3.5 Family satisfaction evaluation: It was divided into 5 levels

according to the Likert method, with 1 indicating very dissatisfied and 5 indicating very satisfied.

#### **4.Statistical treatment**

SPSS27.0 statistical software was used for analysis, and the count data of each group was expressed as percentage or composition ratio. The X test was used for the percentage or composition ratio between groups. The measurement data of each group was expressed as mean ± standard deviation (x̄-s). Comparison within the group before and after treatment and comparison between the two groups were performed by t-test. P<0.05 was considered statistically significant.

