## **Ethics Batch Number (NTC): LLSL-2022053105**

### **4. Research Methods and Design**

#### **1. Subjects**

Sixty patients with head injury treated in our hospital were selected as subjects, randomly divided into control group and experimental, with 30 cases in each group.

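### The plan does not say which test applies to the five-level GOS and names no ordinal method; an unordered 2 x 5 chi-square test could cost up to about 24 points of power

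*Combined protocol and SAP*

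**What the plan says.** Section 3, Observation indicators, item 3.4, defines the GOS by five ordered levels: "A score of 5 indicates good recovery, 4 indicates moderate disability, 3 indicates disability, 2 indicates a vegetative state, and 1 indicates death". Item 3.5 defines family satisfaction on a five-level Likert scale.

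Section 4, Statistical treatment, is the whole analysis plan. Its first rule is that "the count data of each group was expressed as percentage or composition ratio", and that the chi-square "test was used for the percentage or composition ratio between groups". Its second rule is that measurement data are summarised by mean and standard deviation, and within-group change and "comparison between the two groups were performed by t-test". The threshold is "P<0.05 was considered statistically significant". The section assigns no outcome to either data type, names no rank, ordinal, trend or exact test, and has no rule for small expected counts.

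The sample is 60 patients, "with 30 cases in each group" (section 1, Subjects). The plan gives no expected GOS distribution, effect size or power.

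**The concern.** An ordered five-level outcome that includes death fits neither rule well.

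- **Chi-square on the full composition ratio.** A 2 x 5 Pearson test gives the same result however the five levels are ordered. It spends 4 degrees of freedom on what is essentially a question of direction.
- **Chi-square on a percentage**, for example the proportion with GOS 4-5. This keeps direction but discards the distinctions within each half of the scale.
- **t-test on codes 1 to 5.** This uses the order, but the reported mean difference counts the step from death to vegetative state as equal to the step from moderate disability to good recovery. Nothing in the plan supports equal spacing.

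Two things are at stake. In a trial of 60 patients, an inefficient test may miss a real shift in prognosis. And because the text permits all three routes, which answer different questions with different power, the choice could be made after the results are seen.

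**Working it through.** **Inputs from the plan.** 30 per arm (section 1, Subjects); significance level 0.05 (section 4, Statistical treatment); five ordered GOS levels (item 3.4).

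**Assumptions, because the plan gives no figure.** Two-sided testing; all 60 patients analysed; six control distributions; a proportional shift with odds ratio (OR) from 1 to 6. The plan states no power, so there is no figure of its own to reproduce.

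**Generating the experimental arm.** If c is the control probability of being at or below a level, the experimental probability is c / (c + OR × (1 − c)). Example with control 15/25/30/20/10% for GOS 1 to 5 and OR 3:

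- c = 0.15 gives 0.15 / (0.15 + 3 × 0.85) = 0.056.
- c = 0.40 gives 0.40 / (0.40 + 3 × 0.60) = 0.182.
- c = 0.70 gives 0.70 / (0.70 + 3 × 0.30) = 0.4375.
- c = 0.90 gives 0.90 / (0.90 + 3 × 0.10) = 0.75.

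Differencing gives about 5.6/12.6/25.6/31.2/25.0%.

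**Tests compared**, 20,000 simulated trials per scenario: Pearson chi-square on the 2 x 5 table (degrees of freedom = non-empty levels − 1); tie-corrected rank-sum; t-test on codes 1-5; chi-square on GOS 4-5 versus 1-3.

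Power (%):

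| Control GOS 1-5 (%) | OR 1.5: chi-square / rank | OR 2: chi-square / rank | OR 3: chi-square / rank | OR 3: t-test | OR 3: split at 4-5 |
|---|---|---|---|---|---|
| 15/25/30/20/10 | 8.4 / 13.6 | 16.9 / 31.8 | 41.1 / 65.0 | 64.9 | 54.4 |
| 10/20/30/25/15 | 8.1 / 14.3 | 17.0 / 31.6 | 40.7 / 64.6 | 64.3 | 56.3 |
| 20/20/20/20/20 | 8.8 / 13.8 | 18.4 / 32.1 | 42.2 / 65.3 | 65.2 | 56.9 |
| 10/30/35/15/10 | 8.1 / 13.6 | 16.3 / 31.2 | 39.5 / 64.0 | 64.1 | 51.7 |
| 5/25/40/20/10 | 7.7 / 14.1 | 16.1 / 31.2 | 39.4 / 63.6 | 63.4 | 54.5 |
| 30/10/30/20/10 | 8.5 / 14.1 | 17.5 / 31.9 | 41.2 / 64.5 | 64.3 | 54.6 |

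**Gaps against the rank test.**

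- 2 x 5 chi-square: 5.0-6.4 points at OR 1.5, 13.7-15.1 at OR 2, 23.1-24.5 at OR 3, then falling to 10.3-11.4 at OR 6.
- Split at GOS 4-5, at OR 3: from 64.6 − 56.3 = 8.3 to 64.0 − 51.7 = 12.3 points. Five of the six distributions lie between 8 and 11.
- t-test: within 1 point throughout the proportional-shift scenarios.

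**Analytic check.** At noncentrality 6.0, a 1-df chi-square test has 68.8% power and a 4-df test 47.0%. The gap is 21.8 points, the largest over the noncentralities tried, and close to the simulated maximum.

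**Non-directional shift.** Control 15/25/30/20/10% against 15/5/50/20/10%: chi-square 43.8%, rank-sum 12.1%. Here the unordered test is the more powerful one.

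**Sparse cells.** With equal arms, the expected count in each cell is half the level total. All ten reach 5 only if each level holds at least 10 of the 60 patients, against an average of 60 / 5 = 12. At least one expected count fell below 5 in 81-100% of simulated tables, and more than 20% of cells did so in 25-96%. With no true difference, the chi-square test still rejected in only 4.0-4.8% of trials.

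**The case against.** The strongest reply is that the plan never sends GOS to the chi-square test. GOS is described as a numeric score beside GCS and CRS-R, so the t-test is at least as natural a reading, and on that reading no power is lost. Even within the chi-square rule, a percentage with GOS 4-5 fits the wording as well as a 2 x 5 table does. All of this stands. A reader might infer that the trial as planned gives up 24 points of power; the documents do not support that, because the figure needs one particular reading and an assumed effect near its worst case.

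A reader might also infer that sparse cells make the chi-square P value untrustworthy. Small expected counts are likely, but the null rejection rate stayed at or slightly below the nominal 5% in these scenarios, so that argument should not be used.

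Other replies stand in part. The plan names no primary outcome and its aims centre on recovery of consciousness, so GOS is one indicator among several. The satisfaction score was not simulated; for it, the point is only that the test is undefined. A proportional-odds model brings an assumption of its own. None of this supplies the missing choice of test or a method suited to an ordered outcome.

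**Conclusion.** The concern holds in conditional form. The certain part needs no assumption: the plan does not assign GOS or satisfaction to either rule and names no method for ordered categories, so tests with different power and different estimands are all permitted.

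The size is conditional on the route and on assumed control distributions and proportional odds at 30 per arm. For a 2 x 5 chi-square test the loss against a rank test is modest at OR 1.5 and peaks at about 24 points near OR 3. A split at GOS 4-5 loses roughly a third to a half of that peak. A t-test loses nothing in power, and the objection to it is interpretive. If the treatment moved patients between levels without a consistent direction, chi-square could do better. This should be corrected, but it does not invalidate the trial.

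**What to change.** In section 4, Statistical treatment, name one GOS analysis before the data are seen. Either of these would do:

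- proportional-odds logistic regression with baseline GCS as covariate, death as the lowest level, reporting the common odds ratio with 95% confidence interval; GCS is already assessed for entry (inclusion criterion 2);
- the Wilcoxon rank-sum test.

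Use the rank-sum test for family satisfaction. Keep chi-square, or Fisher's exact test when expected counts are small, for binary outcomes such as awakened yes/no.

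In the same edit, reconcile the GOS time point. The opening of section 3 lists GOS among the comparisons at 4, 6 and 8 weeks, while item 3.4 places it 1 month after treatment. Naming a test does not define the analysis until this is settled.

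The cost is a sentence or two and a routine procedure in standard software, with no extra data. The small downside is that the common odds ratio relies on the proportional-odds assumption.

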This study aims the common disturbance of consciousness in patients with head injury, combined with the application of median nerve electrical stimulation and auricular pressing needle therapy, to observe and analyze the efficacy difference between control group and the experimental group, with the purpose of accelerating the recovery of patients' consciousness, shortening the awakening time, and improving the effect of coma recovery in patients with injury, and to alleviate the economic pressure of society and families to the maximum extent.

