##### **1.1 Inclusion criteria**

- ① All patients with disturbance of consciousness after brain injury;
- ② Stable vital signs no obvious bleeding, GCS score of 4-8 points;
- ③ No severe organ failure, normal heart function;
- ④ Course of disease within 10 days
- ⑤ No history of head injury, no history of pregnancy and epilepsy.

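### Within-arm before-after t-tests stand beside the between-group t-test at the same 5% level, with no statement that only the between-group comparison bears on efficacy; that comparison also leaves entry GCS unused

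*Combined protocol and SAP*

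**What the plan says.** The analysis plan is one paragraph, Combined protocol and SAP, section 4 (Statistical treatment). For measurement data it states: "Comparison within the group before and after treatment and comparison between the two groups were performed by t-test". One threshold covers every test: "P<0.05 was considered statistically significant". It does not say which comparison decides efficacy, whether the between-group test uses follow-up scores or changes, or whether any covariate is used.

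Other sections bear on the point:

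- Section 3 (Research idea) gives the purpose as to "observe and analyze the efficacy difference between control group and the experimental group".
- Section 1.1 (Inclusion criteria) requires "Course of disease within 10 days" and "GCS score of 4-8 points".
- Section 2 (Intervention measures) describes background care in the control arm: "Conventional treatment methods were adopted, including surgery, drug therapy, nutritional support, Chinese medicine, and acupuncture, as well as prevention of complications". Median nerve stimulation is added to it. For the experimental arm: "In addition to conventional rehabilitation treatment methods and median nerve electrostimulation, auricular acupuncture was combined".
- Section 3 (Observation indicators) sets the comparison times: "After 4, 6, and 8 weeks of continuous intervention, the awakening conditions, including GCS, GOS outcome evaluation, CRS-R scores".

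**The concern.** The trial asks whether ear needles add anything to care that both arms receive. A before-after test in the experimental arm does not answer this. It combines spontaneous recovery after recent injury, conventional care, nerve stimulation and any needle effect. The control arm's before-after test contains all of these except the last. Only the contrast between arms removes what they share.

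Because the plan sets both kinds of test side by side at one threshold, a report could present a significant gain in the experimental arm and a non-significant one in control as evidence for the needles. Nothing in the plan rules that out. The between-group test in the same trial may well be non-significant, and the plan does not say which result would then stand.

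A smaller matter is that the between-group t-test makes no use of the baseline score, although eligibility requires a GCS at entry.

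**Working it through.** **Inputs from the document.** 30 patients per arm (section 1, Subjects); the 5% threshold (section 4, Statistical treatment); entry GCS 4-8 (section 1.1). The plan gives no power, effect size or SD, so there is no figure of its own to reproduce. **Assumptions.** Tests are two-sided (the plan does not say); the common gain, the baseline-outcome correlation and the follow-up SD are shown as ranges.

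**Step 1: within-arm tests with no treatment effect.** Let both arms gain *e*, in units of the SD of change. The probability *p* that one arm's paired t-test shows significant improvement comes from the noncentral t distribution with 29 df and noncentrality *e*√30. The arms are independent, so P(experimental significant, control not) = *p*(1 − *p*), and P(both significant) = *p*². The first cannot exceed 0.25.

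| Common gain *e* | *p* | Experimental only | Both arms |
|---|---|---|---|
| 0.3 | 0.355 | 23% | 13% |
| 0.36 | 0.479 | 25% | 23% |
| 0.5 | 0.754 | 19% | 57% |
| 0.6 | 0.888 | 10% | 79% |
| 0.8 | 0.988 | 1% | 98% |

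**Step 2: what the peak means in GCS points.** If entry GCS were uniform on 4-8, its SD would be √2 = 1.41. Assume a follow-up SD of 3 to 4.5 and a correlation of 0.2. The SD of change is then √(9 + 2 − 2 × 0.2 × 3 × 1.41) = 3.05, or √(20.25 + 2 − 2 × 0.2 × 4.5 × 1.41) = 4.44. A gain of 0.36 SD is 1.1 to 1.6 points; a gain of 0.8 SD is 2.4 to 3.6 points.

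**Step 3: the between-group test in those discordant trials.** In simulated null trials showing the experimental-only pattern, the between-group t-test is non-significant in about 90% at gains of 0.3 to 0.5 SD, about 85% at 0.6, and 63-71% at 0.8. The range at 0.8 covers change-score and follow-up-score versions of the test. Over all null trials the between-group test rejects in about 5%, as it should.

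**Step 4: baseline adjustment.** The unadjusted t-test on follow-up scores has 58 df and standard error √(2/30) in SD units. ANCOVA has 57 df, and its standard error is multiplied by √((1 − ρ²)(1 + 1/56)), where 1/56 is the average cost of estimating the covariate slope. Power again comes from the noncentral t.

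| Analysis | Detectable at 80% power (SD) | Power at 0.6 SD | Change in power |
|---|---|---|---|
| t-test, unadjusted | 0.736 | 62.8% | |
| ANCOVA, ρ = 0.1 | 0.739 | 62.4% | −0.4 points |
| ANCOVA, ρ = 0.2 | 0.727 | 63.7% | +0.9 |
| ANCOVA, ρ = 0.3 | 0.708 | 66.1% | +3.3 |
| ANCOVA, ρ = 0.5 | 0.643 | 74.4% | +11.6 |
| ANCOVA, ρ = 0.7 | 0.530 | 88.7% | +25.9 |

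**The case against.** The stated purpose is a difference between arms, section 3 (Observation indicators) speaks of comparing outcomes, and section 4 plans a between-group test that is valid under randomisation. On this view only a clarifying sentence is missing. This largely stands. A reader might infer that the plan intends to judge efficacy from within-arm P values; the document does not say so. The purpose is nevertheless an aim and not an analysis rule, and section 4 leaves the two kinds of test unranked.

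A reader might also take one in four as the plan's false-positive rate. It is not. It is the maximum for one pattern, reached at a common gain of about 1 to 1.6 GCS points on the assumed SDs. The more both arms improve, the rarer the pattern. Large gains do not rescue the within-arm test, however: at 0.8 SD it is significant in 99% of null trials in either arm, so it says nothing about the needles. Equally, a non-significant between-group result in a null trial is the planned safeguard working, provided it is the result that counts.

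On adjustment, the document gives no correlation, and restricting entry to GCS 4-8 may keep it low. At 0.1, ANCOVA is marginally worse than the t-test. A reader might infer that the unadjusted test is biased or that adjustment would clearly raise power; neither is supported. Finally, no section lists a baseline visit. That entry GCS is on record is an inference, though a safe one, from the eligibility rule and the before-after test.

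**Conclusion.** The point holds as a missing decision rule together with an inexpensive improvement in precision. No planned test is invalid. Within-arm P values cannot isolate the ear needles, and the plan does not say that they carry no weight for efficacy. With no treatment effect, the misleading experimental-only pattern occurs in 1% to 25% of trials over common gains of 0.3 to 0.8 SD. This rests on 30 analysed patients per arm, two-sided tests and equal gains in both arms.

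The case for ranking the comparisons does not depend on any correlation. The case for ANCOVA is weaker: its benefit runs from none at 0.1 to substantial only at 0.5 or above, and the document does not show which applies. The change is worth making because it costs almost nothing. It should not be read as resolving multiplicity: GCS and CRS-R would still each be compared at three time points, with no primary outcome or time point named.

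**What to change.** In section 4 (Statistical treatment):

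1. State that the between-group comparison decides efficacy.
2. Report within-group changes descriptively, as mean change with 95% CI and no P value.
3. At each planned time point, compare follow-up GCS and CRS-R between arms by ANCOVA with entry GCS as covariate. Use baseline CRS-R for CRS-R if it is recorded. Report the adjusted difference with 95% CI.

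Naming the model also settles whether follow-up or change scores are compared. Choosing a primary outcome and time point is a separate decision that this wording does not make.

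The cost is a few sentences and one degree of freedom. The patients, follow-up values and software stay the same, and no new assessment is needed when entry GCS is the covariate.
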